## 4.6.4.4. Regulatory Reporting Requirements for Medical Device Incidents

- The Investigator will promptly report all incidents occurring with any medical device provided for use in the study for the Sponsor to fulfil the legal responsibility to notify appropriate regulatory authorities and other entities about certain safety information relating to medical devices being used in clinical studies.
- The Investigator, or responsible person according to local requirements (e.g., the head of the medical institution), will comply with the applicable local regulatory requirements relating to the reporting of incidents to the IRB/IEC.

#### 4.7. Data Sources and Collection

Relevant mandated visits and data time points for the study are presented in the Data Collection Schedule provided below. All data elements will be collected from information reported by the children/parents/carers and will be prospectively recorded by the Investigator for the purposes of the study.

**Table 2 Schedule of Assessments** 

Procedure	Visit 1 Baseline (a)	Visit 2 End of run-in randomisation	Visit 3 End of intervention period	Visit 4 End of extension period	End of study
	Day 0	Day 28 ± 7	Day 56 ± 7	Day 84 ± 7	
Informed consent	X				
Inclusion/exclusion criteria	X	X			
Demographics	X				
Medical history	X				
Characteristics of NE	X				
Height and weight(b)	$X^{(b)}$				
Full physical examination(c)	X				
Prior absorbent pants/nappies used	X				
Adverse events (d)	X	X	X	X	X
Concomitant medication to treat AE	X	X	X	X	X
Daily Diary					>

Procedure	Visit 1 Baseline (a)	Visit 2 End of run-in randomisation	Visit 3 End of interv ention period	Visit 4 End of extension period	End of study
Review of daily diary (e)		X	X	X	X
Randomisation		X			
Dispensation of DryNites® and bed mats	X	X	X		
Patient/parents/carers QoL and sleep questionnaires (f)		X	X	X	X
Absorbent Pants Clinical Trial Questionnaire	X				
DryNites® Clinical Trial Questionnaire		$X^{(g)}$			
Reason for discontinuation					X

NE: Nocturnal Enuresis

- (a): Baseline visit can be performed remotely.
- (b): In case a remote visit is performed, height/weight will not be recorded.
- (c): In case a remote visit is performed, a full physical examination will not be recorded. In this scenario, the Investigator must check the medical records and/or interview the parent/carer to investigate history of congenital abnormalities of the urinary tract, history of surgery on the urinary tract, and history of verified urinary tract infections before determining eligibility.
- (d): AEs, SAEs and Medical Device Incidents are collected from ICF signature onwards.
- (e): Review of diary data by the Investigator/treating physician.
- (f): For participants who meet the randomisation criterion.
- (g): For all participants at the end of the run-in period.

#### 4.7.1. Visit 1 - Baseline Visit

The baseline visit can be performed remotely.

Informed consent/assent will be obtained prior to participation in the study. Participants will be assigned a unique patient identifier once consent is signed. Eligibility for the study will be assessed at the initial screening visit on Day 0 and confirmed at the randomisation visit on Day  $28 \pm 7$ .

The Investigator or delegate will:

- Provide the participant with a study identification card
- Create the patient's and parents/carers profiles on the EDC for record of questionnaires and diary entries
- Show the diary functionality to the participants/parents/carers, explain and remind about the importance of compliance with study assessments
- Provide the parents/carers with all materials (DryNites® and absorbent bed mats) required for the 4-week run-in period after enrolment.

The following assessments will be performed at baseline for all consented patients:

• Eligibility criteria, date of informed consent

- Demographics: age, sex, race
- Height, weight, BMI (calculated)\*
- Medical history
- Characteristics of NE: the questionnaire adapted from the established Clinical Management Tool detailed in Table 3 will be completed by the Investigator
- Physical examination\*\*
- Prior brand and type of absorbent pants used
- Administration of the Absorbent Pants Clinical Trial Ouestionnaire
- Any AE occurred since ICF signature, if relevant
- Concomitant medication for AEs, if relevant.

Table 3 Questionnaire for determination of nocturnal enuresis presence, adapted from the Clinical Management Tool

Determination of monosymptomatic NE	Exclude	Include
Age (years)	<4 or >8	4–8
Does the child wet the bed at night?	No	Yes
Has the child experienced any dry period for ≥6 months since birth?	Yes	No
Number of wet nights per week	1–6	7
Is the child receiving any treatment for NE?	Yes	No
Has the child received any treatment for NE in the previous 6 months?	Yes	No
Exclusion of underlying bladder dysfunction (Non-monosymptoma	atic NE)	
Daytime wetting	Yes	No
>8 bladder voids per day	Yes	No
Voiding postponement (>2 times per day)	Yes	No
Sudden and urgent need to urinate (>2 times per day)	Yes	No
Holding manoeuvres observed (>once per day)	Yes	No
Need to strain to pass urine (>once per day)	Yes	No
Interrupted urine stream or several voids one after the other	Yes	No
History of urinary tract infection	Yes	No
Any additional illness related to kidneys and spinal cord	Yes	No
Constipation (<3 bowel movements per week) or faecal soiling	Yes	No
Psychological, behavioural or psychiatric problems (including attention deficit hyperactivity disorder, attention deficit disorder, autism etc.)	Yes	No
History of motor and/or learning disabilities or delayed development	Yes	No

\*In case a remote visit is performed, height/weight will not be recorded.

\*\* In case a remote visit is performed, a full physical examination will not be performed. In this scenario, the Investigator must check the medical records and/or interview the parent/carer to investigate history of congenital abnormalities of the urinary tract, history of surgery on the urinary tract, and history of verified urinary tract infections before determining eligibility.

Clinical Management Tool, in Vande [name] et al, 2012

#### 4.7.2. Direct-to-Patient Data Collection

The following data will be collected daily for all enrolled patients using an electronic diary from the morning following the baseline visit until discontinuation from the study:

- Were absorbent pants worn? Yes/No/Another brand
- Was the bed mat used? Yes/No/Another brand
- Did the child have an NE event? Yes/No
- How was the NE event managed? One response to be selected: Child slept through the night; child awoke but did not take any action; child awoke and changed pants/changed bed/visited toilet but did not disturb parents; child awoke and woke parents.

#### 4.7.3. Visit 2 - End of Run-in/Randomisation Visit

The following assessments will be performed for all patients at end of run-in/randomisation visit (Day  $28 \pm 7$ ):

- Any AEs occurred since the baseline visit
- Concomitant medications for AEs
- Review of diary data
- DryNites® Clinical Trial Questionnaire (all participants)
- Patient and parents/carers QoL and sleep questionnaires: PinQ, WHOQOL, PDSS,
   CIS (for randomised participants only)

The Investigator will confirm NE frequency by assessing the data recorded in the diary by the participants/parents/carer at the randomisation visit (Day  $28 \pm 7$ ). Only participants who experience NE at a frequency of 7 nights per week during the last week of the run-in period (no dry night) will be randomised.

#### 4.7.4. Visit 3 - End of Intervention Period/Enrolment in Extension Period Visit

The following assessments will be performed for all enrolled patients at the end of the core study period:

- Any AEs occurred or ongoing since the previous visit
- Concomitant medications for AEs
- Review of the diary data
- PROs: PinQ, WHOQOL, PDSS, CIS
- Willingness to participate in the extension period
- Complete the Disposition/End of study form for participants not willing to enrol in the extension

#### 4.7.5. Visit 4 - End of Extension Period Visit

The following data will be collected for all enrolled patients at the end of the extension period:

- Any AEs occurred or ongoing since the previous visit
- Concomitant medication for AEs
- Review of the diary data
- PROs: PinQ, WHOQOL, PDSS, CIS

## 4.7.6. Disposition/End of Study

The following data will be collected for all enrolled patients at the time of discontinuation:

- AEs occurred since the previous visit. All AEs ongoing at the time of discontinuation will be followed up until resolution or stabilisation of for 30 days, whichever occurs first
- Concomitant medication for AEs
- Review of diary data
- PROs: PinQ, WHOQOL, PDSS, CIS (for participants who were randomised)
- Date of completion/discontinuation
- Primary reason for discontinuation

#### 5 STATISTICAL METHODS

#### 5.1. Statistical Hypotheses

The statistical hypothesis behind the present study design is the equivalence in rate of spontaneous resolution of NE at  $56 \pm 7$  days between discontinuing and continuing nocturnal use of DryNites® absorbent pyjama pants in children with NE. The margin is set to 2/7 wet nights with an expected proportion of 0.95 and 0.80 wet nights, respectively for continuing and discontinuing use of absorbent pants group. The power is set to 99%.

## 5.2. Sample Size

The sample size calculation is based on simulations according to the following procedure: During the 4-week trial period, there will be twice as many children assigned to the intervention group (discontinuation of absorbent pants) compared with the control group (continued use of DryNites®). For each child in the 2 groups, the number of wet nights during the last week is simulated from a binomial distribution with n=7 as the number of trials and probabilities  $p_0$ =0.95 and  $p_1$ =0.80 indicating the risk of a wet night in the control group and intervention group respectively. The simulations are conducted for various sample sizes, each with 1000 simulated data sets. For each data set the risk difference ( $p_0$ - $p_1$ ) is estimated with a corresponding 95% confidence interval (CI). The 2 methods are said to be equivalent with an equivalence margin  $\delta$  if CI of the risk difference lies within the interval [- $\delta$ ,  $\delta$ ]. This is done for different values of  $\delta$ , here for  $\delta$ =2/7, 3/7, 4/7 corresponding to 2, 3 and 4 dry nights per week (i.e., 5, 4, and 3 wet nights per week). Finally, the power for each sample size is calculated as the number of estimates with a CI lying within the defined interval [- $\delta$ ,  $\delta$ ] out of the 1000 simulations.

Fifteen participants are needed in the continuation arm to obtain a power of 99%. This means that a total of 3x15=45 participants are needed at randomisation (due to the 2:1 randomisation). Fifteen additional participants are added to this number (total of 60 participants) to compensate for dropouts/poor compliance during the trial, and for the participants who will be excluded at randomisation because they did not fulfil the criteria of 7 wet nights per week (screen failures). Additionally, the primary endpoint will be analysed separately for the 2 age groups (4–<6 and  $\geq$ 6–8 years of age) and therefore 60 participants will be needed for each age group (total 120 participants).

The same simulations have been performed with different definitions of equivalence, i.e., 5, 4, and 3 wet nights per week and this showed approximately the same number of participants needed for obtaining 100% power. Similarly, if the assumption of 15% reduction in the control arm is changed to 20% it does not change the conclusions either.

As such, 120 participants should be recruited, with approximately half of the participants should be in the younger age group, age 4-<6 years, and half of the participants should be in the older age group,  $\ge 6-8$  years.

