#### 1.2. Rationale

No evidence is available to suggest that the use of absorbent pants slows resolution of NE, or that removal of absorbent pants improves resolution of NE.

Furthermore, there are currently no evidence-based recommendations supporting the use of absorbent pants for management of NE, and the lack of clear guidance supporting the benefits

of using absorbent pants may have resulted in many children and their families not benefitting from this possible solution.

As such, this study aims to demonstrate that continuing nocturnal use of absorbent pants in children with NE does not have a negative impact on the rate of spontaneous resolution of NE, compared with discontinuing use of absorbent pants. It also aims to show that use of absorbent pants may provide additional QoL and sleep benefits for both children and their parents/carers. The age group 4–8 years is recommended for inclusion in this study, as this will involve families who become interested in resolving enuresis before or shortly after starting school. Age 8 years was chosen as the cut-off, as by this age many children who continue to experience NE will have been exposed to treatment of some sort.

Nocturnal Enuresis can vary in severity from 1 night per week to every night per week. This study will evaluate children with severe NE, who usually experience NE every night of the week. Although the rate of spontaneous resolution is low in this group, it is the most appropriate and reliable population to study. Children who experience NE for <7 nights per week are a heterogeneous group whose rate of NE may vary weekly; as such, many confounding variables could affect the trial results if this population was used.

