15.1.3 Primary Analysis of Primary Variable

The primary objective of this study is to demonstrate if discontinuation of nocturnal use of absorbent pants in children with NE has any impact on the rate of spontaneous resolution of NE, compared with continued use of absorbent pants, over a period of 4 weeks.

The primary effectiveness analysis will be performed for the PAS comparing the 95% CI for the difference between the means of average wet nights at the end of intervention period for the 2 groups with the predefined margin ($\delta = 2/7$). If the CI lies strictly within [- δ , + δ], the study hypothesis will be demonstrated. Difference in means and CI will be generated by PROC TTEST for independent groups.

Primary analysis will be also repeated by age groups (4–<6 years and \geq 6–8 years).

Document:	Y:\Kimberly-Clark\DryNites\Documentation\SAP\DryNites_SAP_v1.0_20200203		
Author:	[name]	Version Number:	1.0
		Version Date:	03Feb2020
Template No.: F	RWI_TP_BIOS0013 Revision 1		Reference: RWI_WI_BIOS0015
Effective Date:	15Jun2018		

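### The 99% power per age group assumes that children within an arm differ only by binomial chance; the planned child-level t-interval with 15 vs 30 children gives 91% or 97% at best, and less if a child's nights are correlated

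*Protocol*

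**What the plan says.** Protocol 5.1 gives the design inputs. On the margin it states: "The margin is set to 2/7 wet nights". The assumed wet-night rates are 0.95 if pants are continued and 0.80 if they are stopped. On power it states: "The power is set to 99" per cent.

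Protocol 5.2 describes the simulation. For each child, "the number of wet nights during the last week is simulated from a binomial distribution with n=7 as the number of trials", using a single probability for each arm. Equivalence is declared when the 95% confidence interval of the risk difference lies inside the margin. The section does not name the interval method, or say whether nights or children are the unit. It concludes: "Fifteen participants are needed in the continuation arm to obtain a power of 99" per cent. With 2:1 allocation this means 45 children. Fifteen more are added for dropout, poor compliance and screen failure, and the resulting 60 is doubled because the primary endpoint is to be analysed in each age group.

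The analysis is set in the SAP. Section 15.1.1 counts wet nights per patient over the last 7 days of the intervention period. Section 15.1.3 says "Difference in means and CI will be generated by PROC TTEST for independent groups". It does not say whether the pooled-variance or the Satterthwaite interval will be used. Section 15.1 runs the primary analysis separately by age group; section 15.1.3 runs it on the whole Primary Analysis Set and then repeats it by age group.

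Neither document gives a within-child correlation, a child-level standard deviation or an allowance for overdispersion.

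**The concern.** The simulation and the analysis do not share a variance model. Under Binomial(7, p) with one p per arm, child-level proportions vary by p(1−p)/7 and no more. If some children move towards dryness while others stay wet, they vary by more than that. The t-interval on children will then widen, and the chance of falling inside the margin will drop. The trial asks about spontaneous resolution, which happens to individual children, so extra-binomial variation is plausible at the endpoint.

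The 99% is the only operating characteristic the plan states, and it is tied to the age-group size on which the total of 120 is built. If an age group missed equivalence, a reader who trusted the 99% could take the miss as a sign of a real difference, when the design alone could produce it fairly often.

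**Working it through.** **Inputs.** From Protocol 5.1 and 5.2: p0 = 0.95 (continue), p1 = 0.80 (discontinue), margin 2/7 = 0.2857, two-sided 95% interval, 15 vs 30 children. The margin is read on the proportion scale, that is 2 nights in 7, in line with Protocol 5.4.6. Assumed, because the documents give no value: within-child correlation ρ from 0 to 0.5, modelled as beta-binomial.

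**Step 1: the plan's own figure.** With independent nights and 15 vs 30 children, a Wald 95% interval on all nights lies inside the margin in 97.7% of simulated trials (Newcombe 97.8%). In 300 repeats of a 1000-trial simulation, the central 95% of results ran from 97.0% to 98.6%, with a maximum of 99.0%. So 99% is reproduced to within 2 points. A 90% interval gives 99.0%; a 95% interval first reaches 99% at about 18 vs 36.

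**Step 2: normal approximation at child level.**

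V = [p0(1−p0)/n0 + p1(1−p1)/n1] × (1 + 6ρ)/7, and power ≈ Φ[(2/7 − 0.15)/√V − 1.96].

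- 15 vs 30, ρ = 0: V = (0.0475/15 + 0.16/30)/7 = 0.001214, √V = 0.0348, power ≈ Φ(3.89 − 1.96) = 97.3%.
- 15 vs 30, ρ = 0.2: V is multiplied by 2.2 to 0.002671, √V = 0.0517, power ≈ Φ(2.63 − 1.96) = 74.7%.
- 30 vs 60, ρ = 0.1: V = (0.0475/30 + 0.16/60) × 1.6/7 = 0.000971, √V = 0.0312, power ≈ Φ(4.35 − 1.96) = 99.2%.

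**Step 3: simulation of the planned t-interval, 15 vs 30.** Repeat runs agree to within about one point.

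| ρ (assumed) | Pooled-variance | Satterthwaite |
|---|---|---|
| 0 | 91% | 97% |
| 0.05 | 81% | 92% |
| 0.1 | 72% | 86% |
| 0.2 | 58% | 74% |
| 0.3 | 47% | 63% |
| 0.5 | 35% | 49% |

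The pooled-variance interval does worse because the larger arm is also the more variable one. Its variance dominates the pooled estimate and is then applied to the smaller arm as well.

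**Step 4: other sample sizes, pooled-variance / Satterthwaite.**

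| Comparison | ρ = 0 | ρ = 0.2 | ρ = 0.5 |
|---|---|---|---|
| One age group, all 60 evaluable (20 vs 40) | 97.6% / 99.4% | 71% / 85% | – |
| Both age groups, after planned losses (30 vs 60) | – | 89% / 96% | 63% / 79% |
| Both age groups, no losses (40 vs 80) | – | 96% / 99% | 77% / 89% |

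At ρ = 0.3, 40 vs 80 gives 90% / 97%.

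**Stress case.** Suppose the 0.80 arises because 1 − 0.80/0.95 = 15.8% of discontinuing children become fully dry and the rest stay at 0.95. Then 15 vs 30 gives about 31% / 50%, and 40 vs 80 gives 67% / 86%.

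**The case against.** The strongest reply is that the plan contains no arithmetic slip. Its figure reproduces to within 2 points by its own method, and with independent nights the Satterthwaite interval gives almost the same answer. That stands: changing the interval costs little unless the pooled-variance version is used. The large losses come from a correlation that the documents do not supply, so a reader should not conclude that this trial has 58% or 74% power. Those figures are conditional on ρ = 0.2. The plan's zero is equally unsupported, however, and it is the most favourable value in the range.

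Two stronger readings are tempting but not supported. First, Protocol 1.2 says "Children who experience NE for <7 nights per week are a heterogeneous group whose rate of NE may vary weekly", which might be taken as the plan conceding heterogeneity at the endpoint. The sentence explains why such children were not chosen as the study population; it does not address variation after randomisation. Second, the all-or-none case might be taken as the expected outcome. Protocol 1.2 calls spontaneous resolution low in this group, and Protocol 5.4.6 says it is unlikely to be seen much within 4 weeks. It is a stress case only.

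It is also fair to say that the t-interval picks up whatever between-child variation exists, so an equivalence conclusion drawn from it stays valid. SAP 8.1 says no confirmatory testing is planned. How a missed age-group result would be read is a judgement; no passage prescribes it. None of this rescues the 99%. It is still presented as the power for 15 vs 30, and the planned analysis does not reach it there at any correlation examined, including zero.

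**Conclusion.** The concern holds as a fault in the stated power, not in the analysis. With the plan's margin and rates, 15 vs 30 children give 91% (pooled-variance) or 97% (Satterthwaite) when nights are independent. Power falls to 81% / 92% at a correlation of 0.05 and to 58% / 74% at 0.2. The correlation range and the beta-binomial form are assumptions. The direction of the effect does not depend on them; its size does.

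An age group reaches 99% only if all 60 children are evaluable, nights are independent and the Satterthwaite interval is used. The comparison across both age groups is better placed, but it does not carry 99% without qualification. After the planned losses it is near 99% only at low correlation, around 0.1 by the normal approximation. With no losses it reaches 99% at 0.2 with Satterthwaite only, and falls short at 0.3.

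**What to change.** In the synopsis, Protocol 5.1 and 5.2, and SAP 4.1, replace the 99% with power re-simulated under the planned child-level t-interval. SAP 8.1 repeats the margin and rates but states no power, so it needs no change for this point.

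The restated text should:
- name the PROC TTEST interval to be used, pooled-variance or Satterthwaite;
- give power over a range of within-child correlation, for example 0 to 0.5, labelled as an assumption, with the all-or-none pattern as a stress case;
- report like for like: one age group at 15 vs 30 and 20 vs 40, and the whole Primary Analysis Set at 30 vs 60 and 40 vs 80;
- say that the age-group comparisons do not have 99% power at the planned evaluable size, and that the combined comparison has more but reaches 99% only at low correlation or without losses.

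The cost is one re-run simulation, edited text and a less favourable stated power. Sample size, margin, rates and endpoint stay as they are.

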#### **Statistical Considerations:**

The analysis sets will be the following: Screened Set (all patients enrolled), Randomised Set, Primary Analysis Set (all patients randomised without major violation of the clinical investigation plan), Extension Set.

Demographic and baseline characteristics, disease history, physical examination and medical history will be summarised with appropriate descriptive statistics by group and separately for age subgroups on Screened and Randomised Sets.

The Absorbent Pants Clinical Trial Questionnaire administered at study entry, and the DryNites® Clinical Trial Questionnaire administered at the end of the run-in period, will be analysed descriptively for the Screened Set.

Direct-to-patient data will be analysed descriptively at each assessment along with applicable change from baseline on Randomised and Primary Analysis Sets.

The primary outcome (i.e., average number of wet nights in Week 4 of the core study period) will be analysed on the Primary Analysis Set comparing the 95% confidence interval (CI) for the difference between the means of the 2 groups with the predefined margin ( $\delta = 2/7$ ). If the CI lies strictly within [- $\delta$ , + $\delta$ ], the study hypothesis will be demonstrated. The primary outcome will be then presented by age group (4–<6 years,  $\geq$ 6–8 years).

Secondary outcome will be presented by group on Randomised Set. Frequency distribution and descriptive statistics, when applicable, will be provided by visit for each item of questionnaires, while summary statistics for total scores, domain scores and changes from baseline will be provided as applicable for the PinQ, the WHOQoL-BREF, PDSS and CIS. The effect size will also be presented as descriptive statistics of ratio between the change from baseline and baseline standard deviation (SD). The percentage of patients with change from baseline ≥0.5 time the SD will also be provided. For applicable questionnaires, a covariance analysis model (ANCOVA) with baseline PROs value as covariate will be performed. Group comparisons will be performed for the difference in least squares means (LSMean) at Day 56±7 days. The same analysis will be repeated using a repeated measure model to assess the extension period effects.

Full Study Title: Effect of use of DryNites® absorbent pants on the rate of spontaneous resolution of					
paediatric nocturnal enuresis (NE)					
Phase:	Phase:   Phase IV     Type:   Clinical Investigation				

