# 4.3. Study Population

The study will aim to randomise approximately 120 participants aged 4-8 years from a total of 7-12 sites in 3 countries (Belgium, Denmark, and the United Kingdom) over a 30-month enrolment period. Children/parents/carers actively seeking help for NE can be recruited via specialist centres, clinician visits, referrals, and collaboration with primary care providers (PCPs).

Sites that are routinely involved in the care and treatment of patients with NE will be targeted for recruitment. Selection criteria and basic site information (e.g., site size, Investigator specialty, site type) will be collected via a site qualification survey.

All children/parents/carers actively seeking help and those who had not previously considered medical assistance, will be considered for study participation, and assessed for eligibility according to the defined selection criteria. A screening log will be maintained by each site to record the disposition of consecutive patients, potentially eligible for study participation.

The following options will be considered to reach the target enrolment:

- Advertising through notices in hospitals and PCP clinics may attract participants to the study
- Newspaper advertising could also be used.

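### Protocol 5.2 says a 20% instead of a 15% reduction leaves the conclusions unchanged; at the 2/7 margin power falls from about 98% to about 65% per age group (about 92% with age groups combined), and the sentence names the wrong arm

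*Protocol*

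**What the plan says.** Protocol 5.1 sets a margin of 2/7 and a power of 99%, "with an expected proportion of 0.95 and 0.80 wet nights, respectively for continuing and discontinuing use of absorbent pants group". Protocol 5.2 describes the simulation behind the sample size. For each child, "the number of wet nights during the last week is simulated from a binomial distribution with n=7 as the number of trials", with p0 = 0.95 and p1 = 0.80 "indicating the risk of a wet night in the control group and intervention group respectively". Allocation is 2:1, and equivalence is declared when the 95% confidence interval for p0 − p1 lies within ±δ. Margins of 2/7, 3/7 and 4/7 were tried.

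The result reported is: "Fifteen participants are needed in the continuation arm to obtain a power of 99"%. That makes 45 children per age group. Fifteen more are added for dropout, poor compliance and screen failure, giving 60, and this is doubled because "the primary endpoint will be analysed separately for the 2 age groups".

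The derivation closes with two robustness remarks. One is that other equivalence definitions need about the same number of children. The other is that "if the assumption of 15% reduction in the control arm is changed to 20% it does not change the conclusions either".

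**The concern.** The 15% can only be the gap between 0.95 and 0.80. Raising it to 20 points moves the assumed truth much closer to the margin. The distance from the true difference to 2/7 falls from 0.286 − 0.150 = 0.136 to 0.286 − 0.200 = 0.086, and power at a fixed sample size should drop sharply.

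A 20-point gap is 7 × 0.20 = 1.4 nights per week, still inside the 2-night margin. It is a case in which the trial ought to be able to show equivalence, and the protocol tells its readers that it can. If the remark is wrong, they are misled about the chance that a truly equivalent result will be missed.

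The remark also places the reduction in the control arm, although the protocol fixes the control (continuation) arm at 0.95.

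**Working it through.** **Inputs, all from Protocol 5.1 and 5.2.** Seven independent nights per child; p0 = 0.95; p1 = 0.80; δ = 2/7 = 0.2857; two-sided 95% interval for p0 − p1; 15 continuation and 30 discontinuation children per age group.

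**Reading of the 20% case (an assumption, since no probabilities are given).** p0 = 0.95 and p1 = 0.75.

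**Normal approximation, to show the mechanism.** With 7 × 15 = 105 and 7 × 30 = 210 nights:

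SE = √[p0(1 − p0)/105 + p1(1 − p1)/210], and power ≈ Φ[(δ − (p0 − p1))/SE − 1.96].

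- Base case: SE = √(0.0475/105 + 0.16/210) = 0.0348. Then 0.1357/0.0348 = 3.89, and Φ(3.89 − 1.96) = 97.3%.
- 20-point case: SE = √(0.0475/105 + 0.1875/210) = 0.0367. Then 0.0857/0.0367 = 2.34, and Φ(2.34 − 1.96) = 64.7%.

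**Exact calculation.** This sums the binomial probabilities of all outcomes whose Wald 95% interval lies within ±2/7.

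| Continuation : discontinuation | 0.95/0.80 | 0.95/0.75 | 0.95/0.76 | 1.00/0.80 |
|---|---|---|---|---|
| 15:30, per age group, stated size | 97.8% | 65.5% | 75.9% | 86.8% |
| 20:40, per age group, all 60 evaluable | 99.5% | 77.7% | 86.7% | 93.9% |
| 30:60, age groups combined | 99.99% | 91.6% | 96.5% | 98.7% |
| 40:80, combined, all 120 evaluable | >99.99% | 97.1% | 99.2% | 99.8% |

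The first column reproduces the plan's own 99% to within about one percentage point at 15:30. The last two columns are milder readings of 20%: a relative reduction (0.95 × 0.80 = 0.76), and a fall from 1.00 to 0.80. Neither reaches 99% for a single age group; both do so only with all 120 children combined.

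**Number needed for 99% at 2/7.** The smallest continuation arm is 18 at 0.95/0.80, 39 at 0.95/0.76 and 50 at 0.95/0.75.

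**Interval method.** Protocol 5.2 does not name one. At 15:30 and 0.95/0.75, Newcombe gives 67.9% and Agresti–Caffo 69.7%. The t intervals that the SAP's PROC TTEST can produce give 62.9% (unequal variances) and 45.5% (pooled variance). None comes near 99%.

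**Other margins.** At 15:30 and 0.95/0.75, power exceeds 99.9% at both 3/7 and 4/7. The remark is therefore true for the margins that were not chosen.

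**Arm label.** Protocol 5.2 assigns p0 to control and p1 to intervention, and defines the intervention as discontinuation. The lower rate is therefore the discontinuation rate, not the control rate.

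**The case against.** **Literal reading.** The sentence gives no pair of probabilities and speaks of the control arm. If p0 is lowered to 0.80 with p1 = 0.80, power at 15:30 is 99.99%; with p0 = 0.75 it is 99.5%. The sentence would then hold. But this contradicts the plan's own p0 = 0.95, and 0.80/0.80 contains no 15-point gap to enlarge. What stands is that 65.5% depends on treating the arm label as a slip, so 0.95/0.75 must be stated as an assumption.

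**This is a re-implementation.** The described method gives 97.8% at 15:30, and 1000 simulated data sets would return 99.0% or more with probability of only about 0.002. The sponsor's code may therefore differ in some undocumented way. A 90% interval, for instance, gives 99.0% at the base case. The protocol specifies 95%, however, and even with 90% the 20-point case falls to 76.5%.

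**Which analysis governs.** The synopsis, Protocol 5.4.2 and SAP 15.1.3 apply the decision rule to the whole Primary Analysis Set; in the synopsis, "The primary outcome will be then presented by age group". Protocol 4.3 says "The study will aim to randomise approximately 120 participants aged 4-8 years". On that reading the loss is modest: 91.6% to 97.1%. Against this, Protocol 5.2 doubles the sample so that each age group can be analysed separately, and SAP 15.1 says the primary analysis is done by age group. The conflict is real, so both sets of figures are needed.

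**Consequence.** Low power makes equivalence harder to claim and does not encourage a false claim. That is correct, and it limits the finding to the stated robustness.

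**Conclusion.** The concern holds. At the adopted margin of 2/7, moving from a 15-point to a 20-point difference does change the conclusion. Power per age group at the stated size falls from 97.8% to 65.5%, so a truly equivalent result would be missed about 35% of the time instead of about 2%. With the age groups combined, power is 91.6% (30:60) to 97.1% (40:80). The continuation arm needed for 99% is 50, against the stated 15. The arm named in the sentence is also wrong.

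These figures assume p0 = 0.95 and p1 = 0.75, independent nights within a child as in the protocol's simulation, and a 95% Wald interval; the alternatives examined do not restore the claim for a single age group. The base-case 99%, the decision rule and its error rate are not in dispute.

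**What to change.** 1. In Protocol 5.2, delete the sentence or replace it with wording such as: *If the difference between arms is 20 rather than 15 points (0.95 continuing, 0.75 discontinuing), power at margin 2/7 is about 65% per age group (15:30), about 78% if all 60 are evaluable (20:40), and about 92% (30:60) to 97% (40:80) with the age groups combined.* This also removes the wrong arm label. If the original remark is kept, limit it to margins 3/7 and 4/7.
2. Label every power figure as per age group or combined, and reconcile SAP 15.1 with SAP 15.1.3 on which analysis is primary.
3. Secondary: state that the 99% assumes independent nights within a child, and name the unequal-variance interval in SAP 15.1.3, because the choice matters under 2:1 allocation (62.9% against 45.5% at 15:30 and 0.95/0.75).

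The cost is rewording one sentence in each document and one short re-run of the simulation. No added children are requested; the only downside is a less favourable stated power.
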